5. You should report any concerning signs or	a. True		
symptoms that you	b. False		

Survey Question	Answer	N	%
notice after your child is treated with Strimvelis to your child's specialist doctor.	c. I don't know		
KRM 1: Gene therapy f	or ADA-SCID and risk of	of blood cancer (e.g. leu	ikaemia)
6. Your child's specialist doctor will	a. True		
check your child's blood for any signs of	b. False		
leukaemia during check-ups.	c. I don't know		
7. Within the last last 6 months, has your child	a. Yes		
been seen by their specialist doctor for	b. No		
follow-up after receiving Strimvelis?	c. I don't know		
If you answered "Yes," approximately how many times have you seen your child's specialist doctor?			
If you answered "Yes,"has your child	a. Yes		
given blood samples at least once within the	b. No		
last 6 months?	c. I don't know		
8. How often should your child be followed	a. At least once a year		
up by his or her specialist doctor?	b. Every 5 years		
	c. Every 10 years		
KRM 2: Autoimmunity			
9. Autoimmunity occurs when the body's	a. True		
immune system sees its own tissues and cells as	b. False		
foreign and attacks these healthy cells.	c. I don't know		
Symptoms may include a high temperature,			

Survey Question	Answer	N	0/0
rash, joint pain, painful or weak muscles, or feeling tired or unwell most of the time. If you are concerned about autoimmunity, you should contact your specialist doctor.			
10. Autoimmunity can occur (select all that apply):	a. Before treatment because of the disease b. After treatment as the immune system is restored		
	c. Both		
KRM 3: Unsuccessful re	esponse to gene therapy		,
11. Gene therapy is designed to treat the	a. True		
immune issues of ADA-SCID, including	b. False		
frequent severe infections.	c. I don't know		
12. Gene therapy is designed to treat non-	a. True		
immune issues such as fatty liver, reduced	b. False		
hearing, or behavioural problems.	c. I don't know		
13. Immune and non- immune issues will be	a. True		
followed up during routine visits by your	b. False		
child's specialist doctor.	c. I don't know		
14. Symptoms such as fever, cough, loose	a. True		
stools, pain on passing urine may suggest	b. False		
infection and should be reported to your specialist doctor	c. I don't know		

Survey Question	Answer	N	0/0
KRM 4: Pregnancy			
15. Strimvelis is not designed to correct the	a. True		
genetic defect in your child's reproductive	b. False		
cells.	c. I don't know		
16. When your child has reached a suitable	a. True		
age, seeking family planning advice is	b. False		
recommended.	c. I don't know		

 Table 8. Summary of Patient/Carer survey results

			Correct answer		
No.	Question	Yes	No	%	
1	Have you received copies of				
	the following educational materials related to Strimvelis?				
	materials related to Strimvells?				
2	Did you read these educational				
	materials about Strimvelis?				
3	Your child's specialist doctor				
	will follow your child's				
	progress regularly over time to				
	check for symptoms related to				
	key risks after treatment with				
	Strimvelis.				
4	There are NO risks associated				
	with Strimvelis treatment.				
5	You should report any				
	concerning signs or symptoms				
	that you notice after your child				
	is treated with Strimvelis to				
	your child's specialist doctor.				
	Total (Q1-5)				
Gene 1	therapy for ADA-SCID and malig	nancy risk (e.g. leuk	kaemia)		
6	Your child's specialist doctor				
	will check your child's blood				
	for any signs of leukaemia				
	during check-ups.				
7	Within the last 6 months, has				

			Correct answer	
No.	Question	Yes	No	%
	your child been seen by their			
	specialist doctor for follow-up			
	after receiving Strimvelis?			
8	How often should your child			
	be followed up by his or her			
	specialist doctor?			
	Total (Q6-8)			
	mmunity			
9	If you are concerned about			
	autoimmunity, you should			
	contact your specialist doctor.			
10	Autoimmunity can occur			
	(select all apply)?			
	Total (Q9,10)			
	ccessful response to gene therapy			
11	Gene therapy is designed to			
	treat the immune features of			
	ADA-SCID, such as frequent			
	severe infections.			
12	Gene therapy is designed to			
	treat non-immune			
	characteristics such as fatty			
	liver, reduced hearing, or			
12	behavioural problems.			
13	Immune and non-immune			
	features or characteristics will			
	be followed up during routine			
	visits by your child's specialist doctor.			
1.4				
14	Symptoms such as fever, cough, loose stools, pain on			
	passing urine may suggest			
	infection and should be			
	reported to your specialist			
	doctor.			
	Total (Q15-16)			
Pregn				
15	Strimvelis is not designed to			
	correct the genetic defect in			
	your child's reproductive cells.			
16	When your child has reached a			
	suitable age, seeking family			
	planning advice is			
	recommended.			

Table 9. Summary of patients yearly follow up and number of blood samples taken during this time (Q7)

WWEpi Project number: PRJ2678/205881

Sub-question	Answer	N (%)
If you answered "Yes," approximately how many times have you seen your child's		
specialist doctor?		
If you answered "Yes," within the last 6 months, has your child	Yes	
given blood samples at least once within the last 6 months?	No	
The same same same same same same same sam	I don't know	

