8.3.3. Outcome definitions

This study will assess the proportion of parents/carers and referring HCPs at six months post treatment with Strimvelis that understood the possible risks relating to:

Safety concerns (KRM topics):

- 1. Malignancy due to insertional oncogenesis (e.g. leukaemia, myelodysplasia)
- 2. Autoimmunity
- 3. Unsuccessful response to gene therapy
- 4. Pregnancy

Other areas of interest:

- Requirement for long-term monitoring
- Receipt of the patient treatment alert card

The proportion of parents/carers and referring HCPs who acknowledge receipt of routine and additional risk minimization measures (e.g., SmPC/PIL, educational materials, Patient Alert Card) will be assessed as a measure of implementation.

The type of medical specialty and experience of referring HCPs will be summarized.

The primary outcome of these surveys is the proportion of parents/caregivers and referring HCPs that provide correct responses to a series of questions concerning the specific risks associated with Strimvelis.

Sufficient understanding of a key risk message can be assumed if at least 80% or more respondents correctly answer all questions that are included within that particular key risk message [ISPE White Paper 2016].

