8.5. Study size

All parents/carers and referring HCPs from patients enrolled in the Strimvelis product registry will be invited to complete the surveys. The study will recruit for approximately two years until 10 referring HCPs and 10 parents/carers have completed their respective surveys (length of study may vary contingent upon product uptake).

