8.7.1. Essential analysis

A frequency distribution of responses to each question (the number of respondents who give an answer to each question) will be presented. Summary statistics will be prepared describing the proportion of parents/carers and referring HCPs for whom questionnaires were returned relative to the total number of parents/carers and referring HCPs of patients eligible for enrolment into the study.

For the analysis population, the proportion of participants answering each question correctly and incorrectly will be summarized. In case of multiple choice questions, the number and proportion of participants reporting each response will be provided.

For the analysis population, the proportion of correct answers to survey questions overall and by risk category will be summarized.

Table shells are presented in Annex 2.

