Please answer based on your knowledge of Strimvelis as informed by the Strimvelis Educational Materials, including the product Summary of Product Characteristics (Product Label).
3. Strimvelis is recommended as first-line therapy for any patient affected by ADA-SCID.
Please select one response.
a. True
b. False
c. I don't know
4. Strimvelis is indicated for the treatment of patients with severe combined immunodeficiency due to ADA deficiency, for whom no suitable HLA matched related stem cell donor is available.
Please select one response.
a. True
b. False
c. I don't know
5. Strimvelis is contraindicated in patients with a history of previous gene therapy.
Please select one response.
a. True
b. False

c. I don't know

CONFIDENTIAL

WWEpi Project number: PRJ2678/205881

6. Patients eligible to receive treatment with Strimvelis should have a bone marrow harvest for stem cell back-up at least 3 weeks prior to treatment with Strimvelis. Please select one response. a. True b. False c. I don't know 7. Parents and carers of patients receiving treatment with Strimvelis should be educated on the fact that the patient should not be able to donate blood, organs, tissues, or cells for transplantation. Please select one response. a. True b. False c. I don't know 8. It is recommended that patients treated with Strimvelis are regularly followed up clinically (at least annually). Please select one response. a. True b. False c. I don't know 9. Strimvelis is contraindicated in patients with a current or previous history of leukaemia or myelodysplasia. [KRM 1] Please select one response. a. True b. False

c. I don't know

CONFIDENTIAL

WWEpi Project number: PRJ2678/205881

10. Have you given advice to parents/carers/patients regarding monitoring for signs and symptoms of leukaemia? [KRM1] Please select one response. a. Yes b. No c. I don't know 11. Have you performed blood tests (including red blood cell indices, white blood cell count differential, platelet count, and a routine biochemistry screen) within the first year of a patient's returning from treatment with Strimvelis? [KRM1] Please select one response. a. Yes b. No c. I don't know 12. Regular monitoring for clinical autoimmunity (possibly including tests for auto-antibodies) is recommended. [KRM2] Please select one response. a. True b. False c. I don't know 13. Autoimmunity may be observed during immune reconstitution after gene therapy. [KRM2] Please select one response. a. True b. False

b. No

c. I don't know

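### HCP Q10 and Q11 and parent Q7 record what happened, not what is understood, yet they count towards the all-correct rule for the malignancy message (KRM 1)

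*Protocol*

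**What the plan says.** Section 8.3.3 gives the rule: "Sufficient understanding of a key risk message can be assumed if at least 80% or more respondents correctly answer all questions that are included" in that message. Section 8.5 stops recruitment once "10 referring HCPs and 10 parents/carers have completed their respective surveys". Section 8.7.1 adds that "the proportion of participants answering each question correctly and incorrectly will be summarized", and exempts no question.

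Three questions placed in KRM 1 ask about events:

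- **HCP Q10** (Annex 4): "10. Have you given advice to parents/carers/patients regarding monitoring for signs and symptoms of leukaemia? [KRM1". The options are Yes, No and I don't know.
- **HCP Q11** (Annex 4, same KRM 1 tag): whether a panel of blood tests was performed within the first year of the patient's return. The options are the same.
- **Parent Q7** (Annex 2, Table 7, under the KRM 1 heading): "7. Within the last last 6 months, has your child" been seen by the specialist doctor for follow-up. The options are the same.

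Table 4 puts HCP Q10 and Q11 under its correct-answer columns, in the malignancy total for Q6 to Q11. Table 8 does the same for parent Q7, in the total for Q6 to Q8. Table 9 reports only the two sub-questions of Q7 (number of visits, blood samples), so the Yes/No answer to Q7 stays in the scored block.

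**The concern.** The rule is presented as a measure of understanding, and Section 8.3.3 treats receipt of the materials separately as a measure of implementation. A question about whether advice was given, tests were done or a visit took place has no answer that shows knowledge of the malignancy risk. Because every question in the message must be correct, one truthful No removes a fully informed respondent from the numerator.

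At stake is the meaning of the KRM 1 result. A figure below 80% could reflect who provides follow-up, or when it takes place, with nothing misunderstood. With ten respondents per survey there is little room: two such respondents can be absorbed, three cannot.

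**Working it through.** **Inputs**

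- Threshold 80%, all questions in the message correct (Section 8.3.3).
- Ten completers per survey (Sections 8.2, 8.5 and 8.10).
- Event items in KRM 1: one for parents (Q7, Table 7) and two for HCPs (Q10 and Q11, Annex 4).
- Survey at about six months after treatment (Sections 8.1 and 8.6.3).
- Share q truthfully answering Yes to an event item: not in the protocol. It is an assumption, shown from 0.95 to 0.70.

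**The plan's own figure.** The protocol derives no sample size or power, so the only figure to reproduce is the pass mark: 0.80 × 10 = 8 of 10. Seven of ten is 70%, so three No answers fail the message.

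**Do the items belong to KRM 1?** On the HCP side there are two groupings. Annex 4 and Table 3 place Q9 to Q11 in KRM 1, while the malignancy total in Table 4 runs from Q6 to Q11. Q10 and Q11 are inside both. Parent Q7 lies between Q6 and Q8 in both Table 7 and Table 8.

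**Can an informed respondent truthfully answer No?**

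- HCP Q10: Section 8.2 requires that the HCP has referred a patient, not that the HCP follows one up. A referrer whose patient is followed elsewhere may not have given the advice.
- HCP Q11: the same applies. In addition, the one-year window is still open at about six months, so tests not yet done could still fall within it.
- Parent Q7: a child not seen in the preceding six months gives a No, and a parent choosing "a. At least once a year" at Q8 would not be inconsistent in saying so. Section 8.9 makes this unlikely, since the interview is timed with registry follow-up.

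**Effect on the rule.** Suppose all ten respondents know every knowledge item. KRM 1 then depends only on the event items. With one item:

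P(pass) = P(X ≥ 8), X ~ Binomial(10, q) = 45·q⁸(1−q)² + 10·q⁹(1−q) + q¹⁰

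At q = 0.80 this is 0.302 + 0.268 + 0.107 = 0.678. With two independent items sharing the same q, replace q by q². At q = 0.90, q² = 0.81 and the result is 0.708.

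| q (assumed) | One event item | q² | Two independent event items |
|---|---|---|---|
| 0.95 | 0.99 | 0.9025 | 0.93 |
| 0.90 | 0.93 | 0.81 | 0.71 |
| 0.80 | 0.68 | 0.64 | 0.24 |
| 0.70 | 0.38 | 0.49 | 0.05 |

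Independence is the less favourable case. An HCP who does not follow the patient would probably answer No to both. For positively related items with the same q, the share answering Yes to both lies between q² and q, so the chance of passing lies between the two columns.

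With the event items removed, ten fully informed respondents pass with probability 1.00.

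**The case against.** Several points on the other side have force.

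- **Most children will have been seen.** The six-month window of parent Q7 covers roughly the whole period since treatment, and Section 8.9 ties the interview to registry follow-up. A reader might infer from Q7 and Q8 that many informed parents would fail, or take 0.68 or 0.38 as the expected result. The protocol does not support that: it gives no visit frequency, and q near 0.95 (pass chance 0.99) is at least as plausible for parents.
- **HCPs may well follow the patients.** Section 9.1 speaks of HCPs involved in the registry, and the HCP leaflet is addressed to those giving long-term follow-up. This may raise q, but follow-up is not an eligibility condition, and it does not close the Q11 window.
- **A Yes does not create a false pass.** It is tempting to say that a parent whose child was seen gets credit for nothing. Under the all-correct rule Q6 and Q8 must also be right, so a Yes to Q7 is merely uninformative.
- **No answer key is shown.** That Yes counts as correct is inferred. The correct-answer heading also stands over Q1 and Q2 (materials received and read), so it may be a generic shell. A key could be set in the reporting analysis plan (Section 8.6.2). However, the protocol itself fixes the rule and the KRM 1 membership, and any keying would score an event as knowledge.
- **A failure would not be hidden.** The study is descriptive and shows every item, so a failure driven by Q10 or Q11 could be seen. A reader might infer that the materials would necessarily be judged ineffective; no such consequence is attached to the rule.
- **Practice is legitimate content.** Section 7 also asks whether the measures were successfully implemented. That supports asking these questions, not scoring them as understanding.

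**Conclusion.** The point holds as a scoring fault. As written, the KRM 1 rule mixes knowledge with events in both surveys, and three truthful No answers in ten would fail the message even if everyone were fully informed. The HCP survey is the more exposed, with two such items, an eligibility rule that does not require follow-up, and a window still open when Q11 is asked.

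The size depends wholly on q, which the protocol does not give. The effect is negligible to small if nearly all answer Yes (0.99 with one item and 0.93 with two at q = 0.95). It is large if a fifth do not (0.68 and 0.24). These figures assume perfect knowledge, Yes keyed as correct, independent respondents and, for the two-item figures, independent items with a common q. They illustrate sensitivity and do not predict the result.

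**What to change.** Take parent Q7 and HCP Q10 and Q11 out of the correct-answer columns in Tables 8 and 4 and out of the KRM 1 all-correct rule. Report them as frequencies in a separate practice or implementation block, extending Table 9 to include the Yes/No answer to Q7 itself. State in Section 8.3.3 that the 80% rule applies to knowledge items only.

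This is an edit to scoring and table shells. The questions can stay as they are, and no new data are needed.

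The cost is a thinner KRM 1. For parents it would rest on Q6 and Q8. For HCPs it would rest on Q9 alone under the Annex 4 tags, a single contraindication item, and the report should say so. Rewording HCP Q10 as a knowledge question would offset this. That is optional, and would bring fresh translation (Section 8.4) and a repeat of the readability review (Section 8.8).

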14.2. Figures

None

WWEpi Project number: PRJ2678/205881

15. ANNEX 3: ENCEPP CHECKLIST FOR STUDY PROTOCOLS (REVISION 3)

Adopted by the ENCePP Steering Group on 01/07/2016

The European Network of Centres for Pharmacoepidemiology and Pharmacovigilance (ENCePP) welcomes innovative designs and new methods of research. This Checklist has been developed by ENCePP to stimulate consideration of important principles when designing and writing a pharmacoepidemiological or pharmacovigilance study protocol. The Checklist is intended to promote the quality of such studies, not their uniformity. The user is also referred to the ENCePP Guide on Methodological Standards in Pharmacoepidemiology, which reviews and gives direct electronic access to guidance for research in pharmacoepidemiology and pharmacovigilance.

For each question of the Checklist, the investigator should indicate whether or not it has been addressed in the study protocol. If the answer is "Yes", the section number of the protocol where this issue has been discussed should be specified. It is possible that some questions do not apply to a particular study (for example, in the case of an innovative study design). In this case, the answer 'N/A' (Not Applicable) can be checked and the "Comments" field included for each section should be used to explain why. The "Comments" field can also be used to elaborate on a "No" answer.

This Checklist should be included as an Annex by marketing authorisation holders when submitting the protocol of a non-interventional post-authorisation safety study (PASS) to a regulatory authority (see the Guidance on the format and content of the protocol of non-interventional post-authorisation safety studies). The Checklist is a supporting document and does not replace the format of the protocol for PASS as recommended in the Guidance and Module VIII of the Good pharmacovigilance practices (GVP).

Study title:			
Evaluation of referring HCPs' and parents'/carers	s' understanding of	of specific risks	associated
with Strimvelis™ treatment			

Study reference number:	
GSK2696273	

Section 1: Milestones	Yes	No	N/A	Section Number
1.1 Does the protocol specify timelines for 1.1.1 Start of data collection ¹ 1.1.2 End of data collection ² 1.1.3 Study progress report(s) 1.1.4 Interim progress report(s) 1.1.5 Registration in the EU PAS register 1.1.6 Final report of study results.				7 7 7

45

¹ Date from which information on the first study is first recorded in the study dataset or, in the case of secondary use of data, the date from which data extraction starts.

² Date from which the analytical dataset is completely available.

WWEpi Project number: PRJ2678/205881

\sim	_			٦e			
	_	rn	гт	10	n	rc.	•
-	_			10		LJ	

Section 2: Research question	Yes	No	N/A	Section Number
2.1 Does the formulation of the research question and objectives clearly explain:				
2.1.1 Why the study is conducted? (e.g. to address an important public health concern, a risk identified in the risk management plan, an emerging				8.2
safety issue)	\boxtimes			9
2.1.2 The objective(s) of the study?				
2.1.3 The target population? (i.e. population or subgroup to whom the study results are intended to				10.2
be generalised)	\boxtimes			9
2.1.4 Which hypothesis(-es) is (are) to be tested?			\boxtimes	
2.1.5 If applicable, that there is no a priori hypothesis?				

Comments:			

Section 3: Study design	Yes	No	N/A	Section Number
3.1 Is the study design described? (e.g. cohort, case-control, cross-sectional, new or alternative design)				10.1
3.2 Does the protocol specify whether the study is based on primary, secondary or combined data collection?	\boxtimes			10.3.1
3.3 Does the protocol specify measures of occurrence? (e.g. incidence rate, absolute risk)				10.3.3
3.4 Does the protocol specify measure(s) of association? (e.g. relative risk, odds ratio, excess risk, incidence rate ratio, hazard ratio, number needed to harm (NNH) per year)			\boxtimes	
3.5 Does the protocol describe the approach for the collection and reporting of adverse events/adverse reactions? (e.g. adverse events that will not be collected in case of primary data collection)	\boxtimes			12

Comments:

This is a descriptive study only

Section 4: Source and study populations	Yes	No	N/A	Section Number
4.1 Is the source population described?	\boxtimes			10.2

Section 4: Source and study populations	Yes	No	N/A	Section Number
 4.2 Is the planned study population defined in terms of: 4.2.1 Study time period? 4.2.2 Age and sex? 4.2.3 Country of origin? 4.2.4 Disease/indication? 4.2.5 Duration of follow-up? 4.3 Does the protocol define how the study 				10.2 10.2 10.2 10.2 10.2
population will be sampled from the source population? (e.g. event or inclusion/exclusion criteria)				10.2
Comments:				
Section 5: Exposure definition and measurement	Yes	No	N/A	Section Number
5.1 Does the protocol describe how the study exposure is defined and measured? (e.g. operational details for defining and categorising exposure, measurement of dose and duration of drug exposure)	\boxtimes			10.3.1
5.2 Does the protocol address the validity of the exposure measurement? (e.g. precision, accuracy, use of validation sub-study)				
5.3 Is exposure classified according to time windows? (e.g. current user, former user, non-use)			\boxtimes	
5.4 Is exposure classified based on biological mechanism of action and taking into account the pharmacokinetics and pharmacodynamics of the drug?				
Comments:				
Section 6: Outcome definition and measurement	Yes	No	N/A	Section Number
6.1 Does the protocol specify the primary and secondary (if applicable) outcome(s) to be investigated?				10.3.3
6.2 Does the protocol describe how the outcomes are defined and measured?				10.3.3
6.3 Does the protocol address the validity of outcome measurement? (e.g. precision, accuracy, sensitivity, specificity, positive predictive value,				

WWEpi Project number: PRJ2678/205881

prospective or retrospective ascertainment, use of validation sub-study)				
validation sub-study)				
6.4 Does the protocol describe specific endpoints relevant for Health Technology Assessment? (e.g. HRQoL, QALYS, DALYS, health care services utilisation, burden of disease, disease management)				
Comments:				
Section 7: Bias	Yes	No	N/A	Section Number
7.1 Does the protocol describe how confounding will be addressed in the study?	\boxtimes			10.3.4
